4.2.2 Rationale for Dose Selection/Regimen/Modification

The radioactive dose required to produce acceptable image quality in human brain is not known. The current study will begin the process of determining if specific binding can be reliably measured at acceptable radiation doses in humans.

Nonhuman primate studies and dose selection: A pre-clinical PET study in rhesus monkey has been performed which demonstrated a high uptake of [¹¹C]MK-6884 in the brain with the largest uptake in the striatum, providing a useful specific signal. *In vitro* saturation binding studies with [³H]MK-6884 in monkey and human brain striatum homogenate indicate that similar concentration (Bmax) of M4 receptors may be present in humans and therefore the human M4 PAM receptor density is sufficiently high for [¹¹C]MK-6884 to provide a useful specific signal in *in vivo* PET studies.

As directed by the eCTA Guidance [ICH Topic M3 (R2)], the total dose will not exceed 100 µgs and will not exceed 5 administrations with a washout between doses of 6 or more half-lives. Each dose will not exceed 1/100th of the NOAEL, as determined in a toxicology trial in rats after proper scaling. Dose selection for safety assessment of [¹¹C]MK-6884 was based upon assumptions of tracer specific activity and injection dose. A maximum cumulative mass associated with [¹¹C]MK-6884 to be given to a 60 kg human adult subject undergoing a single PET scan is estimated to be 4.9 µg.

A whole-body distribution PET study conducted with [¹¹C]MK-6884 in three rhesus monkeys suggest that the level of radiation absorbed should allow for multiple doses of [¹¹C]MK-6884 that may be required for clinical PET occupancy studies. Organs found to have high absorbed radiation dose included gallbladder (0.034 ± 0.020 mSv/MBq), small intestine (0.016 ± 0.016 mSv/MBq), and liver (0.014 ± 0.007 mSv/MBq). The overall ED by [¹¹C]MK-6884 was estimated to be 0.0038 ± 0.0002 mSv/MBq, which is in the typical range for ¹¹C-labeled PET tracer.

The preliminary measurement of the radiation absorbed dose from [¹¹C]MK-6884 to Standard Reference Man was estimated with data from these three nonhuman primates. Based on this, administration of one 370 MBq (10 mCi) dose or two 370 MBq (10 mCi) doses of [¹¹C]MK-6884 is predicted to result in a human Effective Dose (ED) of 1.9 mSv or 2.9 mSv, respectively (accounting for 1 WB CT resulting 0.5 mSv/scan in Part I and two head CTs resulting ~0.05 mSv/scan in Part II). Thus the radiation dose to human in the planned studies is predicted to be within acceptable yearly limits (ED < 10 mSv) for healthy subjects. This is thought to represent a dose that conforms to the As Low As Reasonably Achievable (ALARA) principle of radiation exposure. Based on pre-clinical studies this dose should provide the minimum image quality necessary to quantify tracer binding in the brain while minimizing tracer exposure for healthy subjects. This is well below the desired yearly limit of ED = 10 mSv.

[¹¹C]MK-6884 will always be administered in an open-label manner. For each scan, patients/subjects will be administered an anticipated IV dose of ≤ 4.9 µg of MK-6884 based on assumptions of a 6 mCi single injection of a tracer with minimum specific activity of 500 Ci/mmol, as explained in Section 4.2.2.1 - Maximum Doses/Exposure for This Trial. In general, cyclotron produced ¹¹C tracers have been offering specific activity much higher than

500 Ci/mmol. Therefore, the administration of 10 mCi dose of [¹¹C]MK-6884 is anticipated to result in a maximum mass dose below 4.9 µg. The actual doses that will be administered during all parts will be adjusted based on the specific activity not to exceed the maximum mass of 4.9 µg and maximum allowed radiation exposure of 10 mSv per year in Europe or 50 mSv per year in the United States.

Part I is a first-in-human study designed to investigate the safety and tolerability of [¹¹C]MK-6884 and estimate the radiation absorbed. Subjects will be administered a single IV dose of 370 MBq (10 mCi, 4.9 µg) [¹¹C]MK-6884 followed by a series of whole body PET scans, clinical examinations and laboratory safety evaluations. This dose was selected based on the results from whole-body distribution PET studies in rhesus monkeys. The selected radioactive starting dose for Part I of 370 MBq (10 mCi, 4.9 µg) per scan would result in a human ED of 1.9 mSv. The dose in Part I for subsequent subjects may be adjusted downwards or upwards based on mass dose limitation and dosimetry results learned from the initial Part I subjects.

Parts II and III will be initiated if there are no indications of medically meaningful radiochemical toxicity or undue radiation risks observed during Part I based on the initial review of safety data, including the clinical, clinical laboratory, and radiation safety data, as agreed by the Investigator and Sponsor. In Part II, subjects will receive 2 doses of [¹¹C]MK-6884. In Part III, AD patients will receive a single dose of [¹¹C]MK-6884. The administered dose in Parts II and III will be adjusted if indicated by the results from Part I.

As this is a Phase I assessment of MK-6884 in humans, and the pharmacokinetic, pharmacodynamic and safety profiles of the compound are still being evaluated, modifications to the dose or dosing regimen may be required to achieve the scientific goals of the trial objectives and/or to ensure appropriate safety monitoring of the trial subjects. Details of allowed modifications are provided in Section 7.1.5.5 - Trial Design/Dosing/Procedures Modifications Permitted within Protocol Parameters.

4.2.2.1 Maximum Dose/Exposure for This Trial

This study will be conducted under a microdosing paradigm, in accordance with the ICH M3 (R2) guidance. As per Guidance, the total dose should not exceed 100 µg and each dose should not exceed 1/100th of the NOAEL and 1/100th of the pharmacologically active dose after proper scaling.

Dose selection for safety assessment of [¹¹C]MK-6884 is based upon assumptions that a maximum cumulative mass associated with [¹¹C]MK-6884 to be given to a 60 kg human adult subject undergoing a single PET scan would be 4.9 µg. This estimate is derived from the molecular weight of MK-6884 (411.5 kD) and assumptions of a 6 mCi single injection of a tracer with minimum specific activity of 500 Ci/mmol. Therefore, the maximal single human dose for a 60 kg adult human would be 0.08 µg/kg. MK-6884 safety and toxicity studies were designed to assess up to 1000-fold margins from this maximal human single dose.

To support the safety of MK-6884, a 7-day toxicity study in rat has been performed.

MK-6884 was administered IV up to 80 μ g/kg/day (1000x the maximal anticipated human dose). In this study there were no adverse effects attributed to treatment with MK-6884 at any dose. The NOAEL of 80 μ g/kg/day provides a 1000-fold margin over the maximal clinical dose of 4.9 μ g. This is well below the <1/100th of the NOEL and within the ICH M3 (R2) guidance. Thus, toxicology study results provide no contraindications to the conduct of the clinical PET studies with MK-6884.

To support that the maximal clinical MK-6884 dose of 4.9 μ g is also \leq 1/100th of the pharmacologically active dose, an amphetamine-induced hyperactivity assay has been performed, which is a highly sensitive assay to pharmacological inhibition of M4 PAM activity. MK-6884 at 100X the projected maximal clinical single dose of 4.9 μ g did not induce a significant pharmacodynamics effect in rhesus macaque in this amphetamine-induced hyperactivity model. Thus, the results of this non-clinical study support the conduct of clinical PET studies with a maximum MK-6884 dose of 4.9 μ g, consistent with ICH M3(R2) guidance.

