4.1.1 Pharmaceutical and Therapeutic Background

[¹¹C]MK-6884 is a novel PET ligand that is being developed as a clinical research tool to facilitate the clinical development of M4 PAMs for AD. MK-6884 selectively binds to and potentiates M4 receptor at its allosteric site as a PAM, with *in vitro* properties suitable for an M4 PAM PET tracer: high affinity ($K_i < 5$ nM), moderate lipophilicity ($\log P < 3.5$), and low susceptibility for human P-glycoprotein (P-gp) (BA/AB ratio < 2). It has been preclinically qualified for assessment of target engagement of M4 PAMs through determination of the occupancy and efficacy relationship and assessment of changes in cholinergic tone in non-human primates. [¹¹C]MK-6884 is anticipated to enable quantitative measurement of M4 receptor occupancy (RO) in the brain as a function of drug pharmacokinetics (PK).

The dosimetry and test-retest validation study with [¹¹C]MK-6884 will be the first administration of MK-6884 or [¹¹C]MK-6884 in humans. Safety pharmacology, toxicology and radiation safety studies have been performed with [¹¹C]MK-6884 in preclinical species and provide no contraindication to the initiation of clinical trials with in humans with this compound via the IV route.

[¹¹C]MK-6884 is a non-biological, small molecule, low mass, high specific activity tracer that is classified by the Food and Drug Administration (FDA) as a Type 1 radiopharmaceutical [3] and the European Union (EU) as a Class IIb radiopharmaceutical [4] and is suitable for microdosing per ICH M3(R2) guidance for PET tracers.

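### Does planning about 10 mCi per dose break a 4.9 µg mass ceiling that was derived for 6 mCi?

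*Combined protocol and SAP*

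**What the plan says.** Section 4.2.2.1 sets the maximum mass for a single PET scan at 4.9 µg, or 0.08 µg/kg for a 60 kg adult. On the source of the figure it says "This estimate is derived from the molecular weight of MK-6884 (411.5 kD" and adds "assumptions of a 6 mCi single injection of a tracer with minimum specific activity of 500 Ci/mmol". The toxicology and pharmacology margins in that section are stated against this mass.

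The planned activity is higher. Section 4.2.2 reads "The selected radioactive starting dose for Part I of 370 MBq (10 mCi, 4.9" µg), and Table 2 gives about 370 MBq per dose in all three parts, each with at most 4.9 µg.

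Section 4.2.2 restates the 6 mCi basis and then deals with 10 mCi in three steps:

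- Cyclotron-produced carbon-11 "tracers have been offering specific activity much higher than" 500 Ci/mmol.
- A 10 mCi dose therefore "is anticipated to result in a maximum mass dose below 4.9" µg, so the ceiling is expected to hold.
- Whatever the batch, two limits govern what is given. One is mass: "The actual doses that will be administered during all parts will be adjusted based on the specific activity not to exceed the maximum mass" (here 4.9 µg). The other is the yearly radiation limit.

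For later Part I subjects, the same section allows adjustment "based on mass dose limitation and dosimetry results learned from the initial Part I subjects". Section 7.1.5.5 bars any modification from exceeding the mass limit. Section 5.2.1.1 refers dose selection to Section 4.0 and then says that no particular computation is needed to give each subject the right dose. Section 5.2.2 sends preparation and dosing to the site Master Batch Record.

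**The concern.** The ceiling, the planned activity and the assumed minimum specific activity do not fit together if all three are taken as fixed. A batch at 500 Ci/mmol gives 4.9 µg at about 6 mCi, not at 10. The protocol's reassurance is qualitative: a specific activity well above 500, with no number and nothing specific to this tracer or site.

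Section 5.2.1.1 sharpens the worry. Read literally, a statement that no calculation is needed sits badly beside a rule that adjusts each dose on specific activity. If a site followed only the former, a 10 mCi dose from a batch between 500 and about 840 Ci/mmol would exceed the mass for which the preclinical margins are quoted. In a first-in-human trial run under microdose rules, that deserves a check.

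The printed molecular-weight unit adds to the unease, since kilodaltons would put the derived mass in milligrams.

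**Working it through.** **Inputs.** Molecular weight 411.5, activity 6 mCi, minimum specific activity 500 Ci/mmol, ceiling 4.9 µg, body weight 60 kg and rat NOAEL 80 µg/kg/day (all Section 4.2.2.1); planned activity 370 MBq = 10 mCi (Section 4.2.2 and Table 2).

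**Formula.** Mass (µg) = activity (Ci) ÷ specific activity (Ci/mmol) × molecular weight (mg/mmol) × 1000.

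**1. The plan's own figure.** 0.006 ÷ 500 × 411.5 × 1000 = 4.94 µg, and 4.94 ÷ 60 = 0.08 µg/kg. Both match the protocol. With kilodaltons as printed the result would be 4.94 mg. Section 4.1.1 says the tracer "is a non-biological, small molecule, low mass, high specific activity tracer", so the unit is a slip and the calculation used 411.5 g/mol.

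**2. Planned activity at the assumed minimum.** 0.010 ÷ 500 × 411.5 × 1000 = 8.23 µg, and 8.23 ÷ 4.9 = 1.68.

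**3. Specific activity at which 10 mCi meets the ceiling.** 0.010 × 411.5 ÷ 0.0049 = 839.8, about 840 Ci/mmol. Using the unrounded 4.938 µg gives 833.

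**4. What the adjustment rule does below that value.** Allowed activity (Ci) = 0.0049 × specific activity ÷ 411.5.

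| Specific activity (Ci/mmol) | Activity at 4.9 µg (mCi) | Below 10 mCi |
|---|---|---|
| 500 | 5.95 | 40% |
| 600 | 7.14 | 29% |
| 700 | 8.34 | 17% |
| 800 | 9.53 | 5% |
| about 840 or more | 10 | none |

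In every row the mass stays at or below 4.9 µg; what gives way is the activity. The documents do not present any of these low values as an expected batch.

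**5. The stake if the cap were ignored.** At 8.23 µg the dose is 8.23 ÷ 60 = 0.137 µg/kg, and 80 ÷ 0.137 is about 580-fold below the NOAEL, without species scaling. Two such doses in Part II total 16.46 µg, against the 100 µg total in Section 4.2.2.1. The 100-fold pharmacology multiple would fall to 100 × 4.9 ÷ 8.23, about 60-fold. This case arises only if the stated cap is breached.

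**6. The two passages said to conflict.** The first sentence of Section 5.2.1.1 points to Section 4.0, where the adjustment rule stands. Its second sentence concerns the dose for each subject, which reads naturally as excluding weight-based or similar subject-level calculation. It authorises no amount. A dose over 4.9 µg would still fall outside Table 2, Table 9 and Section 7.1.5.5.

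**The case for a change.** The strongest case for a change has four parts.

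- **No headroom in the pharmacology argument.** The assay in Section 4.2.2.1 was run at 100 times 4.9 µg, exactly the multiple required, so the documented justification stops at the ceiling. This is true, and it is a reason for the cap to bind, which it does. It does not show that the cap fails.
- **Reference time and tolerance.** With a half-life of about 20 minutes, specific activity falls quickly, and the protocol does not say when the 500 Ci/mmol applies. The 10% tolerance in Section 7.2.1 would move the threshold to 0.011 × 411.5 ÷ 0.0049 = about 924 Ci/mmol. Both points are correct as arithmetic. But the limit is on the mass administered, so the rule has to be applied at injection, and the tolerance concerns radiation dose and does not relax the mass limit.
- **No named mass check.** Section 9.2.1 mentions radiochemical purity, all necessary quality control and the radiation dose, but not mass. That section also supplies a nonradioactive analytical standard, and Section 7.1.4.4 lists an HPLC system. The Master Batch Record, which is not among the documents, is where such a step would ordinarily be written. Silence in a summary section does not show that the check is absent.
- **Image quality.** Section 4.2.2 admits that the activity needed for acceptable images is unknown, so a reduced dose could give noisier scans. This stands as an uncertainty. The protocol allows for it in part: Section 2.1 permits up to four more Part II subjects if unexpected noise or variability appears.

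What stands is that the figure of about 840 Ci/mmol is not printed, that Section 5.2.1.1 is loosely worded, and that the molecular-weight unit is wrong.

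**Conclusion.** The arithmetic behind the concern is right; the consequence drawn from it is not. A fixed mass cap, an approximate target activity and a rule that trades activity for mass are compatible whatever specific activity a batch has. The 6 mCi and 500 Ci/mmol figures are assumptions that sized the safety studies, and the protocol does not offer them as release criteria for a 10 mCi dose. Printing the 840 Ci/mmol threshold would restate what the rule already implies.

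The residue is clerical. Sections 4.2.2, 4.2.2.1 and 5.2.1.1 must be reconciled in wording, and the molecular-weight unit with them, as ordinary text correction. Which activity, ceiling or specific activity applies is for the sponsor. No planned dose, endpoint, sample size or analysis depends on it.

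The conclusion assumes that sites follow the adjustment rule in Section 4.2.2 and that 411.5 is in g/mol. The documents give no measured specific activity for this tracer, so whether any dose would need reducing cannot be determined from them. If it were needed, the reduction would range from none at about 840 Ci/mmol to 40% at 500.

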4.2.2.2 Rationale for Dose Interval and Trial Design

MK-6884, a PET tracer for non-invasive visualization of M4 PAM, is not considered a compound with higher potential for risk of harm to volunteers according to the publication "Guideline on Strategies to Identify and Mitigate Risks for First-in-Human Clinical Trials with Investigational Medicinal Products" (European Medicine Agency guidance released July 2007). It is not a biological molecule, does not exhibit highly species-specific action, nor is it directed towards immune system targets. Safety assessment toxicity trials and ancillary pharmacology trials with MK-6884 provide no contraindications to the initiation of clinical trials in people with this compound via the IV route. [¹¹C]MK-6884 doses for subsequent subjects may be adapted after analysis of the actual dosimetry results of the initial subject(s) in this part of the study. [¹¹C]MK-6884 administration to subsequent subjects will be separated by at least one day from the initial subject(s). No dose-limiting toxicities were observed in 7-day toxicity trials, and substantial preclinical safety margins were obtained over initial human doses.

4.2.3 Rationale for Endpoints

4.2.3.1 Efficacy Endpoints

In order to assess the potential efficacy of [¹¹C]MK-6884 as a radiopharmaceutical tracer for M4 PAM receptor binding, the following endpoints have been selected to establish the validity and reliability of [¹¹C]MK-6884:

1. In Parts II and III, index/Indices of M4 PAM receptor availability will be determined by kinetic modeling of the dynamic PET data. Indices that may be measured include: (1) total volume of distribution (V_T); (2) non-displaceable binding potential (BP_{ND}); and/or standard uptake value ratio (SUVR). The V_T is the ratio at equilibrium of the concentration of radioligand in a region of tissue to that in plasma. V_T will be assessed using the metabolite corrected tracer plasma curve obtained from arterial blood sampling during the corresponding scan (relative [¹¹C]MK-6884 fraction in plasma), to provide a measure of the radioactive material available to the brain. BP_{ND} is the ratio at equilibrium of specifically bound radioligand to that of a non-displaceable radioligand in tissue. The measurement of BP_{ND} assumes the presence of a reference region (region in the brain devoid of M4 PAM binding site), and does not require arterial sampling. SUVR is a semi-quantitative measure of tracer uptake estimated using a reference region with low/no tracer binding. SUVR is calculated as the ratio of the average tracer uptake over a given time period in the target region relative to a reference region. In order to perform the future studies non-invasively, using the reference region method, further PET studies with arterial sampling after pre-treatment with a M4 PAM (not part of this protocol) will be needed to validate the reference region method for tracer quantification. If needed, additional methods may also be employed, to more robustly characterize the tracer kinetics in both healthy and AD subjects.
2. In Part II, intra-subject T-RT variability of the receptor availability indices will be assessed by comparing the outcome indices of two scans obtained in the same subject ($N \geq 6$). Less than 10% T-RT variability is ideal and less than 20% T-RT variability is acceptable on average for a PET tracer.
3. In Part III, a pre-scan blood sample appropriate for determination of erythrocyte acetylcholinesterase (RBC-AChE) activity and for determination of donepezil or rivastigmine concentration (as appropriate to the AD patient enrolled) will be taken. These samples will enable correlation of the pharmacodynamic effects of the AChEI, as assessed by RBC-AChE activity, with peripheral AChEI concentrations and [¹¹C]MK-6884 binding in AD patients. Collectively, this data will inform the design of a model that can predict the effective dose range of M4 PAMs in clinical development for treatment of behavioral disturbances in AD patients.

4.2.3.2 Safety Endpoints

Systemic Safety

Safety and tolerability will be assessed throughout the study by monitoring subjects for clinical adverse experiences. Physical examinations, vital signs, 12-lead electrocardiograms (ECG) and laboratory safety tests will be performed periodically to detect any medically meaningful effects of the tracer on physiology.

Radiation Safety

This study also includes quantitative assessments of radiation exposure to the whole body and its internal organs, including the brain. In Part I, whole body PET scans will estimate [¹¹C]MK-6884 tracer radiation exposure and organ distribution (Effective Dose Equivalent, Effective Dose and radiation absorbed doses to individual organs).

4.2.3.3 Planned Exploratory Biomarker Research

Planned Genetic Analysis

Understanding genetic determinants of drug response is an important endeavor during medical research. This research will evaluate whether genetic variation within a clinical trial population correlates with response to the treatment(s) under evaluation. If genetic variation is found to predict efficacy or adverse events, the data might inform optimal use of therapies in the patient population. This research contributes to understanding genetic determinants of efficacy and safety associated with the treatments in this study.

4.2.3.4 Future Biomedical Research

The Sponsor will conduct Future Biomedical Research on DNA specimens collected for future biomedical research during this clinical trial.

Such research is for biomarker testing to address emergent questions not described elsewhere in the protocol (as part of the main trial) and will only be conducted on specimens from appropriately consented subjects. The objective of collecting specimens for Future Biomedical Research is to explore and identify biomarkers that inform the scientific understanding of diseases and/or their therapeutic treatments. The overarching goal is to use such information to develop safer, more effective drugs/vaccines, and/or to ensure that subjects receive the correct dose of the correct drug/vaccine at the correct time. The details of this Future Biomedical Research sub-trial are presented in Section 12.2 - Collection and Management of Specimens for Future Biomedical Research. Additional informational material for institutional review boards/ethics committees (IRBs/ERCs) and investigational site staff is provided in Section 12.3.

4.3 Benefit/Risk

Subjects in clinical trials generally cannot expect to receive direct benefit from treatment/vaccination during participation, as clinical trials are designed to provide information about the safety and effectiveness of an investigational medicine.

Additional details regarding specific benefits and risks for subjects participating in this clinical trial may be found in the accompanying Investigators Brochure (IB) and Informed Consent documents.

